### **TRIAL SUMMARY**

Trial Title	Airway Pressure Release Ventilation (APRV) vs conventional ventilation for patients with moderate to severe acute hypoxemic respiratory failure: The RELEASE trial								
Internal ref. number (or short title)	RELEASE								
Clinical Phase	Phase III effectiveness & cost-effectiveness								
Purpose of research	To investigate, using a multi-centre, parallel group, pragmatic, randomised controlled trial design, the clinical and cost effectiveness of early APRV compared to conventional lung protective invasive mechanical ventilation (IMV) in patients with moderate-severe acute hypoxic respiratory failure (AHRF).								
Trial Design	Parallel group randomised controlled trial with internal pilot and cost effectiveness analysis								
Trial Participants	CCU patients with moderate to severe acute hypoxaemic respiratory failure (AHRF)								
Planned sample size	710								
Inclusion Criteria	
 
Age ≥ 18 years
 
Receiving invasive mechanical ventilation
 
Moderate to severe AHRF (PaO2/FiO2 <20kPa with Positive End Expiratory Pressure (PEEP) ≥5 cmH2O assessed at time of screening (or as documented in the medical record in the preceding 2 hours) for trial inclusion
 
Expected to stay on invasive mechanical ventilation for >48hrs
 
								
Exclusion Criteria	
 
Receiving IMV ≥ 60 hours at time of screening as will be unable to deliver early APRV
 
Primary reason for invasive mechanical ventilation is one of the following:         
 
Asthma
 
Severe COPD
 
Pulmonary embolism (massive or sub-massive) (as cause of hypoxaemia is not primarily due to collapse of lung tissue)
 
Existing neuromuscular disease such as Motor Neurone Disease, Guillain Barre or Myasthenia Gravis (as the cause of respiratory failure is not primarily lung-related)
 
 
 
Refractory shock (systolic blood pressure < 90 mmHg, despite fluid administration and vasoactive drugs)
 
Severe hypercapnic respiratory acidosis (pH <7.20 on the arterial blood gas assessed for trial inclusion)
 
Ongoing air leak (e.g. unresolved pneumothorax at time of screening)
 
								

	
 
Traumatic brain injury with uncontrolled intracranial hypertension
 
								
	7. Likely death or treatment withdrawal in next 24 hours								
	8. Home ventilation or home oxygen therapy prior to								
	admission								
Intervention	Airway Pressure Release Ventilation (APRV). APRV is a method								
	of IMV which uses longer inspiration times followed by a brief								
	expiration. The longer inspiration time enables alveolar								
	recruitment and oxygenation while the short expiration time								
	maintains lung volume. This reduces shear-stress damage to the								
	alveoli, whilst maintaining adequate ventilation.								
Control	Standard lung protective IMV								
Follow-up Duration	6 months								
	Objectives								
Primary Outcome	Duration of invasive mechanical ventilation (time from								
	randomisation to first successful unassisted breathing or death)								
Secondary Outcomes	1. All-cause mortality at 2 and 6 months								
	2. Time to first extubation								
	3. Reintubation								
	4. Use of non-invasive ventilation following extubation								
	5. CCU and hospital length of stay								
	6. Serious adverse events up to hospital discharge								
	7. Health related quality of life (EQ-5D-5L) at 2 and 6								
	months after randomisation								
	8. Acute health care use at 2 and 6 months after								
	randomisation								
	We will conduct a within-trial cost-utility analysis from an NHS								
	hospital care perspective								
Statistical methods	Intention to treat and per protocol analyses.								
	Cox proportional hazard regression model to estimate the treatment								
	difference reporting hazards ratios and their 95% confidence intervals								
	(CIs), using both unadjusted and adjusted estimates.								
	Mean difference with 95% CIs using linear regression.								

# LIST OF ABBREVIATIONS/GLOSSARY

AHRF	Acute Hypoxaemic Respiratory Failure
APRV	Airway Pressure Release Ventilation
ARDS	Acute Respiratory Distress Syndrome
ССЛ	Critical Care Unit (both ICU and HDU)
CI	Chief Investigator
Cls	Confidence Intervals
eCRF	electronic Case Report Form
DMC	Data Monitoring Committee
ECMO	Extracorporeal Membrane Oxygenation
HEAP	Health Economics Analysis Plan
HES	Hospital Episode Statistics
HDU	High Dependency Unit
HFNC	High flow nasal cannula
HrQoL	Health-related Quality of Life
ICF	Informed Consent Form
ICNARC	Intensive Care National Audit & Research Centre
ICU	Intensive Care Unit
IMV	Invasive Mechanical Ventilation
ISRCTN	International Standard Registered Clinical/soCial sTudy Number
NIV	Non-invasive ventilation
PaO 2 /FiO 2	Ratio of partial pressure of oxygen in arterial blood (PaO 2 ) to the fraction of
	inspiratory oxygen concentration (FiO 2 )
PBW	Predicted body weight
PEEP	Positive-end expiratory pressure
P HIGH	Positive pressure applied during the inspiratory phase
PI	Principal Investigator
PIP	Peak inspiratory pressure
P LOW	Positive pressure applied during the expiratory phase
PPI	Public and Patient Involvement
QALY	Quality Adjusted Life Year
R&D	Research and Development
RASS	Richmond Agitation Sedation Scale
RCT	Randomised Controlled Trial

REC	Research Ethics Committee
RR	Respiratory rate
SAE	Serious Adverse Event
Тнібн	Time spent in the inspiratory phase
T LOW	Time spent in the expiratory phase
TMG	Trial Management Group
TSC	Trial Steering Committee
VE	Minute Ventilation
Vt	Tidal Volume
VILI	Ventilator Induced Lung Injury

### 1. BACKGROUND

### 1.1 Epidemiology and burden of the condition

Approximately 130,000 adults are admitted to critical care units (CCUs) in the UK each year, 40-45% of whom require invasive mechanical ventilation (IMV).[1] Acute hypoxaemic respiratory failure (AHRF) is the most common reason for IMV and is associated with serious morbidity and a mortality which remains high at ~40%.[2] Although lifesaving, IMV can cause additional lung injury (termed ventilator induced lung injury - VILI).[3]

To minimise ventilator induced lung injury, UK guidelines recommend using IMV with a low tidal volume and low inflation pressure, generally with a short time for inspiration (breathing in) and longer time for expiration (breathing out).[4] However, injured lungs inflate slowly and deflate quickly. Consequently, most injured lungs need more time (i.e., longer inspiration) so that they can achieve a more gradual and complete inflation. A shorter expiration prevents lung collapse and injury. Therefore, the currently recommended method of IMV may perpetuate VILI leading to more days on a ventilator and increased risk of death.

Airway Pressure Release Ventilation (APRV) is an innovative ventilatory strategy available on all CCU ventilators at no additional cost to the National Health Service (NHS). APRV may improve gas exchange and minimise VILI by reducing excessive lung stretch and preventing lung collapse. [5, 6]

### 1.2 Existing knowledge

APRV is one of three interventions not currently standard of care in the NHS (others are corticosteroids and non-invasive ventilation) with evidence of potential effectiveness which requires further study.[7] Four recent systematic reviews (totalling 10 studies, 519 participants) on APRV[8-11] suggest APRV reduces time spent on the ventilator and mortality. One review[9] (7 trials, 405 participants) found an increased number of ventilator free days at day 28 with APRV compared to conventional ventilation (mean difference 5.4 days). Three reviews [9, 10, 12] report a mortality benefit favouring APRV while two report improved gas exchange but no difference in mortality and ventilation free days[11, 13]. One subsequent trial (65 participants)[14] reported no difference in mortality or IMV duration, although median CCU length of stay was 5 days shorter in the APRV arm.

igure 1: Meta-a	analys	nalysis of ventilation duration (unpublished data)						Mean Difference IV, Random, 95% CI	
		APRV			Control			Mean Difference	•
Study or Subgroup	Mean	SD	Total	Mean	SD	Total	Weight	IV, Random, 95% Cl	-
Ibarra-Estrada 2022	9	5.925	45	10	5.185	45	19.9%	-1.00 [-3.30, 1.30]	•
Kucuk 2021	9.84	8.033	32	13.52	12.826	33	14.4%	-3.68 [-8.87, 1.51]	
Maxwell 2010	10.49	7.23	31	8	4.01	32	18.9%	2.49 [-0.41, 5.39]	
Ota 2009	17	17	17	23	20	40	7.2%	-6.00 [-16.18, 4.18]	
Putensen 2001	15	2	15	21	2	15	21.1%	-6.00 [-7.43, -4.57]	
Zhou Y 2017	8	6.67	71	15	11.11	67	18.5%	-7.00 [-10.08, -3.92]	-100 -50 0 50 10
Total (95% CI)			211			232	100.0%	-3.26 [-6.60, 0.09]	Favours [APRV] Favours [control]
Heterogeneity: Tau  =	13 23 0	$hi^2 = 37$	08 df	$= 5 (P \leq$	0.00001	$  ^{2} = 8$	7%		

Heterogeneity: Tau\* = 13.23; Chi\* = 37.08, df = 5 (P < 0.00001); I\* = 87% Test for overall effect: Z = 1.91 (P = 0.06)

To obtain data on IMV duration, we conducted a meta-analysis of the studies reporting IMV duration (Figure 1) and we found that APRV was associated with a mean reduction in IMV duration of 3.3 days (95% CI -6.6 to 0.1 days) (I=87%). However, evidence certainty is low, due to methodological limitations and trial heterogeneity. Most of the trials are small and few primarily recruit patients with moderate AHRF early in the course of IMV. Furthermore, no study to-date has reported on cost-effectiveness of APRV.

### 1.3 Hypothesis

Our primary hypothesis is that adult CCU patients requiring IMV for moderate-severe AHRF will have a shorter duration of mechanical ventilation if ventilated with APRV compared to usual care.

### 1.4 Need for a trial

Many patients require IMV for AHRF which is associated with significant morbidity and mortality which may in part be attributable to the current way IMV is delivered in the NHS. Furthermore, significant NHS costs are incurred to care for these patients (average CCU cost is £1648/day,[15] with an average IMV duration of 6 days). Total costs increase with longer duration of IMV. Therefore, it is likely that optimisation of IMV could reduce lung damage, favour faster healing, thereby reducing IMV duration, mortality, and costs. In addition, survivors of AHRF experience reduced health-related quality of life[16] with many unable to return to previous levels of activity including work and education. This results in substantial costs to the NHS and to society. If APRV reduces the time spent receiving IMV this may shorten time to return to pre-CCU quality of life.

The RELEASE trial addresses a James Lind Alliance Priority Setting Partnership CCU top priority 'What is the best way of preventing lung damage of patients receiving respiratory support?'[17] A NIHR research priority setting exercise highlighted the need for robust UK data on the effect of APRV.[18] Finally, this proposed trial received the 2022 UK Intensive Care Society Research Prioritisation Exercise award (providing £50K pump priming funds) highlighting it as the trial given the highest priority for conduct by the UK CCU community. Our Patient, Public Involvement (PPI work also endorsed the study importance and helped us refine our research questions and the outcomes to be measured.

To inform this proposal, we queried the UK Severe Respiratory Failure Referral Database. Over the last two years 740/3650 (21%) patients were on APRV at referral for extracorporeal membrane oxygenation (ECMO). From Feb to April 2022, we surveyed CCU consultants referring these patients. Of 160 consultants representing 92 of the 128 UK hospitals making referrals to the Severe Respiratory Failure service, we found 108 (80%) used APRV for patients with AHRF, although it was mainly used as a rescue mode (73/108 consultants, 68%). In addition, 83% felt more evidence on APRV was needed and 75% would consider taking part in a trial further highlighting the equipoise in the clinical community [19].

### 1.5 Assessment and management of risk

While APRV is commonly used in the NHS, there is significant variation in its use likely due to the limited evidence for its clinical and cost effectiveness, or absence of harm. If effective, our group will work with clinicians, professional societies, and NICE to implement APRV more widely to improve patient outcomes and reduce NHS costs. If ineffective or harmful, our group will work to de-implement this intervention.

### 2. TRIAL DESIGN

### 2.1 Trial summary and flow diagram

We will conduct a multi-centre, randomised, allocation concealed, controlled, open label, pragmatic, parallel group clinical and cost effectiveness trial with an internal pilot. The internal pilot will run for 8 months in 20 sites (with staggered starts to facilitate site initiation visits and site support). The internal pilot will use identical processes as the main trial and will assess site set-up, screening, participant recruitment, protocol adherence, and cross over rates. Progression criteria are outlined below in section 2.3.1.2. All participants included in the internal pilot will be included in the final analyses.

### **PICO Summary**

[figure not shown]
Population: Patients receiving invasive mechanical ventilation for moderate to severe AHRF

Intervention: Early APRV

Comparator: Standard conventional lung protective invasive mechanical ventilation (no APRV) .

Outcome: Duration of invasive mechanical ventilation from randomisation (primary clinical effectiveness), plus cost-utility at 6-months.

### Figure 2: Trial flow diagram

### 2.2 Trial setting

The RELEASE trial will be conducted in approximately 40 UK CCUs with a proven track record of participating in CCU research. The CCUs must provide evidence that they have access to the trial population, that consultants in the CCU have clinical equipoise for APRV in this clinical setting and agree to maintain trial allocation in patients randomised by their colleagues.

Staff must also demonstrate and document a willingness to comply with the protocol, standard operating procedures, the principles of GCP (Good Clinical Practice) and regulatory requirements and be prepared to participate in training. All new sites will be provided with education on APRV and mentoring on APRV during trial conduct from the research team.

### 2.3 Internal Pilot

The trial will include an internal pilot that will run for 8 months (months 8 to 15 from grant activation) with all participants recruited in the pilot included in final analyses. The pilot will take place in 20 representative sites with a staggered start. We will recruit 78 patients with a target of 0.6 participants /site for the first 5 months and subsequently 0.7/site for the remaining 3 months.

Trial Activity		Trial month (from grant activation)								
	8	9	10	11	12	13	14	15		
Site Activation	4	8	12	16	20	20	20	20		
Participant Recruitment	2	5	7	10	12	14	14	14		
Cumulative Participant Recruitment		7	14	24	36	50	64	78		

### **Table 1: Internal Pilot Recruitment Rates**

The internal pilot will establish our ability to recruit to target, protocol fidelity, crossover rates, and data collection completeness.

During the internal pilot, we will audit screening logs, recruitment rates, reasons for exclusion, protocol fidelity, and crossover rates. We will measure dataset completeness, including completeness of the primary outcome, which we anticipate should be >95% as this is routinely documented in the medical record of all ventilated patients.

### Table 2: Progression Criteria

	Red	Amber	Green
	Unable to	Review screening log &	Progress
	progress to	protocol; adjust protocol &	to main
	main trial	research processes;	trial
		explore additional sites	
% Threshold (patient recruitment	<50%	51-99%	100%
based on 0.7 patients/site/month)			
Recruitment rate/open site/month	<0.4	<0.6	0.7
Number of pilot sites opened	<10	10-19	20
Total number of participants recruited	<40	59-77	78
Total number of participants with crossover	>5%	4-5%	<4%

We will use a traffic light system to guide progression as recommended in best practice guidelines.[20]

Green: Progress to main trial with review of screening logs and protocol addressing any barriers to recruitment.

Amber: Progress to main trial with ongoing site set-up, review of screening logs and protocol deviations, and protocol amendment where necessary. Red: Unable to progress to main trial.

The Data Monitoring Committee (DMC), Trial Steering Committee (TSC), and HTA secretariat will review internal pilot data and make recommendations in terms of trial progression.

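### The pilot progression table's recruitment rows disagree with the pilot's own target of 78 and with each other, and its crossover row has no attainable amber band at exactly 78 participants

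*Protocol*

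**What the plan says.** Protocol section 2.3 sets the pilot target and ramp: "We will recruit 78 patients with a target of 0.6 participants /site for the first 5 months and subsequently 0.7/site for the remaining 3 months". Table 1 lists open sites for months 8 to 15 ("Site Activation 4 8 12 16 20 20 20 20") and planned recruits for the same months ("Participant Recruitment 2 5 7 10 12 14 14 14").

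Table 2 then gives the red, amber and green limits:

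- Percentage of target, labelled "based on 0.7 patients/site/month": red below 50%, amber 51-99%, green 100%.
- Rate: "Recruitment rate/open site/month <0.4 <0.6 0.7", in the order red, amber, green.
- "Total number of participants recruited": red below 40, amber 59-77, green 78.
- "Total number of participants with crossover": red above 5%, amber 4-5%, green below 4%.

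The text below the table says that red means the main trial cannot go ahead. It also says that the traffic lights guide progression, and that the DMC, the TSC and the HTA secretariat review the pilot data and make recommendations. It gives no time window for the rate, no denominator for the crossover percentage, and no rule for rows that show different colours.

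**The concern.** Three rows of Table 2 measure recruitment. With sites opening as planned they are one quantity on three scales, so they should change colour at the same points. They do not, because one row is anchored to a total of 78 and two are anchored to a rate of 0.7, which the plan reaches only in its last three months. Some results also fall in no band and others in two.

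At stake is the clarity of the advice on progression. If the rows disagree when the pilot reports, someone must decide which row governs after seeing the data, and pre-set limits exist to avoid that. The crossover row raises a smaller question of the same kind: whether its amber band can be reached at the planned pilot size.

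**Working it through.** **Inputs.** Open sites by month: 4, 8, 12, 16, 20, 20, 20, 20 (Table 1). Planned rates: 0.6 for five months, then 0.7 for three (section 2.3). Limits from Table 2.

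**Reproducing the target.**
0.6 × (4 + 8 + 12 + 16 + 20) + 0.7 × (20 + 20 + 20) = 36 + 42 = 78. The monthly recruits in Table 1 also sum to 78, so the target is sound.

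**Average rate implied by the target.**
Open site-months: 4 + 8 + 12 + 16 + 20 × 4 = 120.
78 / 120 = 0.65 per open site-month.
A rate of 0.7 throughout would give 0.7 × 120 = 84, and 78 / 84 = 92.9%.

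**Rate limits converted to recruits (120 site-months).**
0.4 × 120 = 48; 0.6 × 120 = 72; 0.7 × 120 = 84.
Red is therefore below 48 by rate but below 40 by total. Rates from 0.6 to below 0.7 (72 to 83 recruits) have no band. Every rate below 0.4 satisfies both the red and the amber condition, because amber has no lower limit.

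**Selected totals, with sites opening on schedule.**

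| Recruits | Rate row | Percentage of 84 | Total row |
|---|---|---|---|
| 39 | 0.325: red (and amber as written) | 46.4%: red | red |
| 45 | 0.375: red (and amber as written) | 53.6%: amber | no band |
| 50 | 0.417: amber | 59.5%: amber | no band |
| 60 | 0.500: amber | 71.4%: amber | amber |
| 75 | 0.625: no band | 89.3%: amber | amber |
| 78 | 0.650: no band | 92.9%: amber | green |
| 84 | 0.700: green | 100%: green | green |

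Taking the percentage against 78 does not rescue the 45-recruit case: 45 / 78 = 57.7%, still amber. The pattern of red on rate, amber on percentage and no band on total holds for 43 to 47 recruits. The percentage row also leaves exactly 50% in no band.

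**Crossover, taking all 78 participants as the denominator.**
3 / 78 = 3.85% (green); 4 / 78 = 5.13% (red). No whole number gives 4-5%.
Across pilot sizes from 40 to 100, the amber band is empty only at 51-59 and 76-79. At 80 the fourth crossover is 5.0% and at 84 it is 4.8%, both amber. If percentages are rounded to whole numbers at 78, three crossovers become 4% and four become 5%. Both are then amber, and red starts at five (6.4%).

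**The case against.** The best defence of the recruitment rows is that the 0.7 rate describes steady recruitment. In months 13-15 the plan is 14 / 20 = 0.7 per site, and section 6.2.1 uses 0.7 as the headline rate while noting 0.6 for the first five months. On that reading the planned ramp is green on rate, and 78 can be read as 100%. A reader might infer from the 0.65 average that recruiting 78 can never be green on rate. The protocol does not support that, because it states no window. The same silence means that the whole-pilot reading is equally open, so the ambiguity stands.

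The intended total band can also be guessed: 51-99% of 78 is 40 to 77, which fits red below 40 and green at 78, so 59 may be a slip. The overlap on rate can be resolved by applying the worst band first. Both are reasonable repairs, but the reader has to supply them. The 45-recruit example does assume sites open on schedule; fewer open site-months would raise the rate.

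It is fair to add that different criteria may properly show different colours. That defence works for recruitment against crossover, but not for three scalings of one recruitment figure.

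On crossover, a reader might infer that a fourth crossover would take the trial from clear progress to a stop. That needs unrounded percentages and a pilot of 76-79 participants, and it treats red as automatic. The protocol has three bodies review the data and presents the lights as guidance.

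**Conclusion.** The recruitment inconsistency is real and follows from the protocol's own figures: 78 against 84 for green, fewer than 40 against fewer than 48 for red, no band for totals 40-58 or for rates from 0.6 to below 0.7, and an amber rate band that contains red. The conversions assume that the rate is averaged over the whole pilot and that sites open as in Table 1. The missing total band and the overlap on rate need neither assumption.

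The crossover point is narrower. Unrounded and with all participants as denominator, amber is empty at the planned 78, but this is specific to 76-79 (and 51-59) participants and disappears under rounding to whole percentages. What is lacking is a stated denominator and rounding rule. The row does not show that the 4% and 5% limits are themselves wrong.

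Nothing here affects the final sample size or the primary analysis. Because the table informs a recommendation and does not trigger a stop by itself, this is a correction to make before the pilot data are reviewed, not a defect that undermines the trial.

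**What to change.** Derive all recruitment rows from Table 1's target of 78, with bands that meet:

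| | Red | Amber | Green |
|---|---|---|---|
| Total recruited | below 40 | 40-77 | 78 or more |
| Percentage of 78 | 50% or less | 51-99% | 100% or more |
| Rate per open site-month over the pilot | below 0.33 | 0.33 to below 0.65 | 0.65 or more |

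The limits agree: 39 / 78 = 50.0%, 40 / 78 = 51.3% and 77 / 78 = 98.7%; 40 / 120 = 0.33 and 78 / 120 = 0.65. Alternatively, keep 0.7 and state that it applies only to months 13-15 (42 recruits over 60 open site-months). In that case the percentage row needs its own stated target, and the rate bands must still be made contiguous.

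For crossover, name the denominator and restate the existing 4% and 5% limits as whole-patient counts that leave an amber band, with the red count agreed by the TSC and the funder. Rounding to whole percentages at 78 would give green up to 2, amber 3-4 and red from 5. It would be tempting to set red at the smallest count whose one-sided 95% lower bound exceeds 5%, which is 8 of 78. That should not be adopted: 8 / 78 = 10.3% doubles the protocol's limit, and it would show red only 52% of the time at a true crossover rate of 10%.

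The cost is one rewritten table and the agreement of the TSC and the funder. Anchoring green at 0.65 does give up a whole-pilot reading of the 0.7 limit, but that reading asks for more than the plan's own target.
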